#### Salivary dmLT-specific IgA by ELISA

Geometric mean titers and corresponding 95% confidence intervals of dmLT-specific salivary IgA determined by ELISA will be presented by treatment arm at Days 1, 8, 15, 22, 29, 36, and 57 for Oral and Sublingual Cohorts and at Days 1, 8, 22, 29, 43, 50, and 71 for Intradermal Cohorts ([Table 39](#), [Table 40](#), [Table 41](#), and [Table 42](#)). Box and whisker plots of log-titers over time will be presented (beginning at [Figure 46](#) and concluding with [Figure 57](#)).

#### Memory B Cell dmLT-specific IgA by ELISpot

The number and percentage of participants with memory B cell dmLT-specific/total IgA response as measured by ELISpot will be presented with exact (Clopper-Pearson) two-sided 95% CI by treatment arm at Days 1, 22, 36, 57, 114, 209, and any time for Oral and Sublingual Cohorts and at Days 1, 29, 50, 71, 128, 223, and any time for Intradermal Cohorts ([Table 69](#) and [Table 70](#)).

### Memory B Cell dmLT-specific IgG by ELISpot

The number and percentage of participants with memory B cell dmLT-specific/total IgG response as measured by ELISpot will be presented with exact (Clopper-Pearson) two-sided 95% CI by treatment arm at Days 1, 22, 36, 57, 114, 209, and any time for Oral and Sublingual Cohorts and at Days 1, 29, 50, 71, 128, 223, and any time for Intradermal Cohorts ([Table 71](#) and [Table 72](#)).

### ASC Homing Markers IgA by EliSpot

The number and percentage of participants with anti-dmLT IgA ASC in circulation expressing gut homing receptors (integrin  $\alpha 4\beta 7$  in the absence or presence of CD62L) measured by EliSpot assay will be presented with exact (Clopper-Pearson) two-sided 95% CI by treatment arm at Days 8, 22, 36, and any time for Oral and Sublingual Cohorts and at Days 8, 29, 50, and any time for Intradermal Cohorts ([Table 57](#) and [Table 58](#)).

### ASC Homing Markers IgG by EliSpot

The number and percentage of participants with anti-dmLT IgG ASC in circulation expressing gut homing receptors (integrin  $\alpha 4\beta 7$  in the absence or presence of CD62L) measured by EliSpot assay will be presented with exact (Clopper-Pearson) two-sided 95% CI by treatment arm at Days 8, 22, 36, and any time for Oral and Sublingual Cohorts and at Days 8, 29, 50, and any time for Intradermal Cohorts ([Table 59](#) and [Table 60](#)).

### Toxin Neutralization by Y-1 cell assay

The number and percentage of participants with  $\geq 4$ -fold rise over baseline in toxin neutralization titers measured by Y-1 cell assay will be presented with exact (Clopper-Pearson) two-sided 95% CI by treatment arm at Days 8, 15, 22, 29, 36, 57, 114, and any time post first dose for Oral and Sublingual Cohorts and at Days 8, 22, 29, 43, 50, 71, 128, and any time post first dose for Intradermal Cohorts ([Table 47](#) and [Table 48](#)). GMTs and corresponding 95% confidence intervals will be reported ([Table 25](#) and [Table 26](#)). Box and whisker plots of log-titers over time ([Figure 16](#), [Figure 17](#), [Figure 18](#), [Figure 19](#), [Figure 20](#), and [Figure 21](#)) and fold-rise over time ([Figure 70](#), [Figure 71](#), [Figure 72](#), [Figure 73](#), [Figure 74](#), and [Figure 75](#)) will be presented.

### dmLT-specific effector and memory T cell responses by CyTOF

The number and percentage of participants with dmLT-specific effector and memory T cell responses as measured by CyTOF will be presented with exact (Clopper-Pearson) two-sided 95% CI by treatment arm at Days 22, 36, 57, 114, 209, and any time post first dose for Oral and Sublingual Cohorts and at Days 29, 50, 71, 128, 223, and any time post first dose for Intradermal Cohorts ([Table 73](#) and [Table 74](#)). Box and whisker plots of % ratio to baseline over time (beginning at [Figure 112](#) and concluding with [Figure 237](#)) will be presented.

### Comparison of Immunogenicity Responses

Spearman rank correlations with 95% CI for peak immunogenicity responses will be presented by Cohort (beginning at [Table 75](#) and concluding with [Table 90](#)).

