## 4. INVESTIGATIONAL PLAN

### 4.1. Overall Study Design and Plan

This is a phase 1, single center, randomized, double-blinded, placebo controlled, dose escalation clinical trial in which 135 healthy males and non-pregnant females ages 18-45 who met all eligibility criteria were to receive 3 doses of either dmLT vaccine or placebo, randomized in a 4:1 ratio. Cohort A and Cohort B participants received study product via oral administration. Cohort C and Cohort D participants received study product via sublingual administration. Cohort E participants received two of three planned doses of study product via intradermal administration prior to the study being terminated due to the COVID-19 pandemic. No participants were enrolled in planned Cohorts F, G, H, or I. Participants were screened by history, physical exam, and clinical laboratory tests, including a urine or serum pregnancy test for women of childbearing potential. A schematic of the planned study design is presented in [Table 1](#).

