### 4.2. Discussion of Study Design, Including the Choice of Control Groups

This study was designed to assess the safety and immune responses of a range of doses of dmLT when administered by the oral, SL, or ID route; in participants residing in an endemic country for ETEC disease. Cohorts A and B received 3 vaccinations via the oral route at escalating doses. Cohorts C and D received 3 vaccinations via the sublingual route at escalating doses. Cohorts E received 2 vaccinations via the intradermal route. Three placebo recipients per cohort were included in the study in order to blind the participants and observer and not as a comparison group.

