#### **4.4.3. Method of Assigning Subjects to Treatment Groups (Randomization)**

The randomization code was prepared by the Statistical and Data Coordinating Center (SDCC), Emmes. Enrollment/randomization were performed through the enrollment module in the electronic data capture system, maintained by the SDCC.

For each cohort, eligible participants were randomized and assigned in a 4:1 ratio to dmLT (n = 12) or placebo (n = 3) groups. The randomization was based on a variable blocked scheme to provide an approximately balanced allocation to the treatment groups during the study.

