## 5. SAMPLE SIZE CONSIDERATIONS

The sample size for each cohort was chosen based on the number of participants deemed appropriate for a Phase 1 study in which the vaccine has had limited experience by the different routes of administration in humans. Sample size was limited to at least 11 evaluable participants and up to 15 participants for each cohort (each of the nine planned cohorts A through I).

The DMID Data and Safety Monitoring Board (DSMB) was scheduled to review cumulative data after Cohorts A through F had completed safety data through 7 days post-third dose of vaccine. At which time each cohort had been expected to have at least 10 evaluable vaccinees (10 per cohort). Among the 10 vaccinees per dose, the absence of a dose-limiting AE provides for an upper 95% exact (Clopper-Pearson) confidence bound of 30.8%. The absence of a dose-limiting AE among 20 vaccinees per route (e.g., combining safety data from Cohort A and B) provides for an upper 95% confidence bound of 16.8%. If at the time of data review, there had been no dose-limiting AEs among 60 vaccinees (e.g., combining safety data from Cohorts A through F), this would have provided an upper 95% confidence bound of 6.0% (Table 4). There were no dose-limiting AEs among the 40 vaccinees (Cohort A through D) who received all three planned doses which provides an upper 95% confidence bound of 8.8%.

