## 8. IMMUNOGENICITY EVALUATION

Immune responses will be summarized at each time point within each route by treatment, pooling participants who received placebo. The number and percentage of participants with responses, as defined for each outcome measure in Section 3.3, will be presented.

All immunogenicity variables will be listed by treatment group, participant, and visit (Listing 7, Listing 8, Listing 9, Listing 10, Listing 11, Listing 12, Listing 13, Listing 14, and Listing 15). N, Geometric or Arithmetic Mean, Standard Deviation, Minimum and Maximum will summarize continuous immunogenicity variables, whereas number and percent will summarize categorical immunogenicity variables. Measurements that are titers or concentrations will be summarized by geometric means and 95% confidence intervals (CI). This study was not designed to test a specific null hypothesis, rather the study is designed to assess the safety and immune responses of a range of doses of dmLT when administered by the oral, SL, or ID route in participants residing in an endemic country for ETEC disease.

Immunogenicity data summaries and analysis will be presented for the mITT and PP populations.

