**Table 74: T Cell Memory Responses by CyTOF – Per Protocol Population**

**Table 75: Correlation of Serum IgA GMFR vs Fecal dmLT-specific IgA GMFR by Time Point and Treatment Group, Immunogenicity Population**

Time Point	Spearman Correlation (95% CI)							
	Cohort A: Oral 5 µg dmLT (N=X)	Cohort B: Oral 25 µg dmLT (N=X)	All Oral Cohorts: Placebo (N=X)	Cohort C: Sublingual 5 µg dmLT (N=X)	Cohort D: Sublingual 25 µg dmLT (N=X)	All Sublingual Cohorts: Placebo (N=X)	Cohort E: Intradermal 0.3 µg dmLT (N=X)	Cohort E: Intradermal Placebo (N=X)
Max Any Time Post Dose 1	x.xx (x.xxx-x.xxx)	x.xx (x.xxx-x.xxx)	x.xx (x.xxx-x.xxx)	x.xx (x.xxx-x.xxx)	x.xx (x.xxx-x.xxx)	x.xx (x.xxx-x.xxx)	x.xx (x.xxx-x.xxx)	x.xx (x.xxx-x.xxx)

Tables with similar format:

**Table 76: Correlation of Serum IgA GMFR vs Fecal dmLT-specific IgA GMFR by Time Point and Treatment Group, Per Protocol Population****Table 77: Correlation of Serum IgA GMFR vs Fecal dmLT-specific/Total IgA GMFR by Time Point and Treatment Group, Immunogenicity Population****Table 78: Correlation of Serum IgA GMFR vs Fecal dmLT-specific/Total IgA GMFR by Time Point and Treatment Group, Per Protocol Population**

**Table 79: Correlation of Serum IgA GMFR vs ALS IgA Titers GMFR by Time Point and Treatment Group, Immunogenicity Population**

Time Point	Spearman Correlation (95% CI)							
	Cohort A: Oral 5 µg dmLT (N=X)	Cohort B: Oral 25 µg dmLT (N=X)	All Oral Cohorts: Placebo (N=X)	Cohort C: Sublingual 5 µg dmLT (N=X)	Cohort D: Sublingual 25 µg dmLT (N=X)	All Sublingual Cohorts: Placebo (N=X)	Cohort E: Intradermal 0.3 µg dmLT (N=X)	Cohort E: Intradermal Placebo (N=X)
Max Any Time Post Dose 1	x.xx (x.xxx-x.xxx)	x.xx (x.xxx-x.xxx)	x.xx (x.xxx-x.xxx)	x.xx (x.xxx-x.xxx)	x.xx (x.xxx-x.xxx)	x.xx (x.xxx-x.xxx)	x.xx (x.xxx-x.xxx)	x.xx (x.xxx-x.xxx)

Tables with similar format:

**Table 80: Correlation of Serum IgA GMFR vs ALS IgA Titers GMFR by Time Point and Treatment Group, Per Protocol Population**

**Table 81: Correlation of Serum IgG GMFR vs ALS IgG Titers GMFR by Time Point and Treatment Group, Immunogenicity Population**

Time Point	Spearman Correlation (95% CI)							
	Cohort A: Oral 5 µg dmLT (N=X)	Cohort B: Oral 25 µg dmLT (N=X)	All Oral Cohorts: Placebo (N=X)	Cohort C: Sublingual 5 µg dmLT (N=X)	Cohort D: Sublingual 25 µg dmLT (N=X)	All Sublingual Cohorts: Placebo (N=X)	Cohort E: Intradermal 0.3 µg dmLT (N=X)	Cohort E: Intradermal Placebo (N=X)

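### Correlations of peak immune responses are planned only in separate columns of 12, 6 and 3 people, and nothing combines the vaccinees

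*SAP*

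**What the plan says.** The plan for these correlations is one sentence in SAP 8.3, under Comparison of Immunogenicity Responses: "Spearman rank correlations with 95% CI for peak immunogenicity responses will be presented by Cohort". It points to Tables 75 to 90. These 16 tables cover eight pairs of measures drawn from serum, fecal, ALS and ASC results, each in two analysis populations.

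The Table 75 shell carries the banner "Spearman Correlation (95% CI" over eight columns: Cohorts A and B, pooled oral placebo, Cohorts C and D, pooled sublingual placebo, Cohort E and, last, "Cohort E: Intradermal Placebo (N=X". The single row uses each participant's highest value at any time after the first dose. No column combines cohorts. No interval method and no minimum group size are given.

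The column sizes follow from other sections:

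- SAP 4.4.3, for each cohort: "eligible participants were randomized and assigned in a 4:1 ratio to dmLT (n = 12) or placebo (n = 3) groups".
- SAP 8: "Immune responses will be summarized at each time point within each route by treatment, pooling participants who received placebo".
- SAP 4.1: "No participants were enrolled in planned Cohorts F, G, H, or I".
- SAP 4.2: "Cohorts E received 2 vaccinations via the intradermal route". The same section says that placebo recipients were included for blinding and not for comparison.
- SAP 5 gives a count below the target of 48 for Cohorts A to D: "There were no dose-limiting AEs among the 40 vaccinees (Cohort A through D) who received all three planned doses".

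**The concern.** The evident use of these tables is to show whether serum, mucosal and cellular responses rise together in the same person. A correlation is hard to estimate from a dozen people and harder still from six or three. Split into eight columns, the analysis produces 16 x 8 = 128 intervals. Of these, 16 x 3 = 48 describe placebo recipients in groups of 3 or 6, and 16 x 1 = 16 of those rest on three people.

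Two things are at stake. One column in every table may not be producible as specified. And the one estimate that would use all the vaccinees is not planned, although the data for it are already collected.

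**Working it through.** **The plan's own precision figures.** The SAP gives none for correlations. Its only precision figures are the safety bounds in SAP 5 and Table 4, the upper two-sided 95% exact limit for zero events, 1 - 0.025^(1/n). This gives 30.85%, 16.84%, 8.81% and 5.96% at n = 10, 20, 40 and 60, matching the stated 30.8%, 16.8%, 8.8% and 6.0%. They confirm the two-sided 95% convention used below but say nothing about correlation.

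**Column sizes at target enrolment.** Five vaccine cohorts (A to E) of 12, so 5 x 12 = 60 vaccinees. Oral placebo 3 + 3 = 6, sublingual placebo 3 + 3 = 6, intradermal placebo 3. The 60 in SAP 5 is a different number: six cohorts, A to F, at 10 evaluable each.

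**Interval by column.** The formula is tanh(atanh(r) ± 1.96/sqrt(n-3)). The documents give no expected correlation, so r is assumed and a range is shown.

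| n | SE of z | r=0.3 | r=0.5 | r=0.7 | r=0.8 | \|r\| needed to exclude 0 |
|---|---|---|---|---|---|---|
| 3 | 1/sqrt(0) | none | none | none | none | none |
| 6 | 1/sqrt(3) | -0.68 to 0.89 | -0.52 to 0.93 | -0.26 to 0.96 | -0.03 to 0.98 | 0.81 |
| 10 | 1/sqrt(7) | -0.41 to 0.78 | -0.19 to 0.86 | 0.13 to 0.92 | 0.34 to 0.95 | 0.63 |
| 12 | 1/sqrt(9) | -0.33 to 0.75 | -0.10 to 0.83 | 0.21 to 0.91 | 0.42 to 0.94 | 0.57 |

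The Bonett-Wright variance for Spearman, (1 + r²/2)/(n-3), gives somewhat wider intervals. At r=0.5 they are -0.57 to 0.94 for n=6 and -0.14 to 0.85 for n=12.

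At n=3 without ties the coefficient can only be -1, -0.5, 0.5 or 1, and the smallest exact two-sided p-value is 0.33.

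In a simulation of 3,000 bivariate normal samples with a true Spearman correlation of 0.5, the Fisher-z interval lay above zero in 16% of runs at n=6, 36% at n=12 and 99% for a single sample of 60.

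**Cohort-stratified estimate.** Combine the within-cohort z values with weights n-3. The standard error is 1/sqrt(sum of (n-3)). With the same r in every cohort, at r=0.5:

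- A to E, 12 each: SE = 1/sqrt(5 x 9) = 1/sqrt(45); 0.25 to 0.69. At r=0.3 it is 0.02 to 0.54, and at r=0.7, 0.52 to 0.82.
- A to E, 10 each: SE = 1/sqrt(5 x 7) = 1/sqrt(35); 0.21 to 0.71.
- A to D, 12 each: SE = 1/sqrt(4 x 9) = 1/sqrt(36); 0.22 to 0.70.
- A to D, 10 each (the SAP's 40, if evenly split): SE = 1/sqrt(4 x 7) = 1/sqrt(28); 0.549 ± 0.370 on the z scale, so 0.18 to 0.73.

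Simple pooling of 60 people would give 0.28 to 0.67 at r=0.5, so stratifying costs little precision.

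**The case against.** The strongest case on the other side runs as follows.

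- **A reader might infer that no column can tell a strong relation from none.** The documents do not support that. Five of the eight columns have a target of 12, where r=0.8 gives 0.42 to 0.94 and r=0.7 gives 0.21 to 0.91. The problem at n=12 is confined to weak and moderate correlation.
- **The SAP does not name Fisher z, so calling the interval not computable at n=3 rests on an assumed method.** This stands as a qualification. Another method might print something, but with four possible values of the coefficient it could not say much.
- **The routes may not share one correlation.** The protocol background asks whether responses differ by route, and SAP 8 summarises within route. A common correlation is therefore an assumption, and a combined figure averages over routes and doses. This stands. It is the reason to retain the intervals in the vaccine cohort columns.
- **A reader might infer that all 60 vaccinees can simply be pooled, or that peaks must first be cut to visits common to all cohorts.** Neither follows. Simple pooling would let dose and route differences create a correlation. A common-visit rule would discard every post-dose-3 peak in Cohorts A to D, because Cohort E had no third dose and no Visits 6 to 9 (SAP 15). It would also depart from the peak defined in the shells. Stratifying by cohort compares each person only with others on the same dose and schedule, so no such rule is needed.
- **The stakes are low.** No objective or endpoint mentions correlation, no hypothesis is tested, placebo is not a comparison group, and individual results are listed. All of this stands and limits the severity.

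**Conclusion.** The concern holds as a limited point about an exploratory analysis. As specified, the interval is not computable by the usual method in one column of each table, is uninformative in two, and is wide for weak to moderate correlation in the other five. A combined estimate would roughly halve the interval at r=0.5, from a width of 0.94 at n=12 (-0.10 to 0.83, before rounding) to 0.69 - 0.25 = 0.44.

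This rests on assumed values of r, on the Fisher-z method, on 10 to 12 usable vaccinees per cohort (50 to 60 in all), and on a correlation similar enough across cohorts to average. Cohort E's peaks follow two doses, so the estimate without it should be visible. The change alters no primary or secondary conclusion.

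**What to change.** In SAP 8.3 and Tables 75 to 90:

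1. Add an all-vaccinee column with a cohort-stratified Spearman estimate and 95% interval, either by combining within-cohort Fisher z values with weights n-3 or by taking ranks within cohort. Keep the peak already defined in the shells. Show the estimate with and without Cohort E.
2. Name the interval method.
3. Keep the intervals in the five vaccine cohort columns, so that a reader can judge whether the cohorts look alike.
4. Drop the interval in the three placebo columns.

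The cost is one added column, shown two ways, and a short methods sentence. No new data are needed, and pooled columns already appear in the disposition and adverse event tables. The downside is that the combined figure averages over routes and doses and should be labelled so.

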## 9. SAFETY EVALUATION

Safety listings will be sorted by treatment group, participant, and timepoint. N, Mean, Standard Deviation, Minimum and Maximum will summarize continuous safety variables, whereas number and percent will summarize categorical safety variables. Safety data will be summarized for the Safety Analysis Population.

### 9.1. Demographic and Other Baseline Characteristics

Summaries of age, sex, ethnicity, and race will be presented by treatment group and overall ([Table 17](#), [Table 18](#), [Table 19](#), and [Table 20](#)). Ethnicity is categorized as Bengali or Other. In accordance with NIH reporting policy, participants may self-designate as belonging to more than one race or may refuse to identify a race, the latter reflected in the case report form (CRF) as “No” to each racial option.

Individual participant listings will be presented for all demographics (Listing [5](#)); pre-existing medical conditions (Listing [6](#)); vital signs and oral temperature (Listing [25](#)); and concomitant medications (Listing [27](#)).

#### 9.1.1. Prior and Concurrent Medical Conditions

All current illnesses and past pre-existing medical conditions will be Medical Dictionary for Regulatory Activities (MedDRA®) coded using MedDRA dictionary version 22.0 or higher. Participants’ pre-existing medical conditions will be presented as individual participant listings (Listing [6](#)).

#### 9.1.2. Prior and Concomitant Medications

Individual participant listings will be presented for all concomitant medications that were started prior to dosing and continuing at the time of dosing (Listing [27](#)).

## 9.2. Measurements of Treatment Compliance

The number of doses of study product administered to participants will be presented by treatment group as part of the participant disposition table ([Table 10](#) and [Table 11](#)).

[Table 14](#) and [Table 15](#) present the number of participants who received first dose, by treatment arm.

## 9.3. Adverse Events

When calculating the incidence of adverse events (i.e., on a per participant basis), each participant will only be counted once and any repetitions of adverse events within a participant will be ignored; the denominator will be the total population size. All adverse events reported will be included in the summaries and analyses.

An overall summary of adverse events by treatment group is presented in [Table 91](#) and [Table 92](#). Unsolicited adverse events occurring in more than 5% of participants in any treatment group are presented in [Table 93](#) and [Table 94](#).

